4.1.2 Exclusion Criteria

Subjects meeting any of the criteria listed below will **not** be eligible for participation in the trial.

1. Known endometriosis stage III-IV (defined by the revised ASRM classification²⁵).
2. One or more follicles >10 mm (including cysts) observed on the transvaginal ultrasound prior to start of stimulation on stimulation day 1 (puncture of cysts prior randomisation is allowed).
3. Known history of recurrent miscarriage (defined as three consecutive losses after ultrasound confirmation of pregnancy (excl. ectopic pregnancy) and before week 24 of pregnancy).
4. Known abnormal karyotype of subject or of her partner. In case the sperm production is severely impaired (concentration <1 million/mL), normal karyotype, including no Y-chromosome microdeletion, must be documented.
5. Active arterial or venous thromboembolism or severe thrombophlebitis, or a history of these events.
6. Known porphyria.
7. Any known clinically significant systemic disease (e.g. insulin-dependent diabetes).
8. Known inherited or acquired thrombophilia disease.
9. Any known endocrine or metabolic abnormalities (pituitary, adrenal, pancreas, liver or kidney) which can compromise participation in the trial with the exception of controlled thyroid function disease.
10. Known presence of anti-FSH antibodies (based on the information available in the subject's medical records).
11. Known tumours of the ovary, breast, uterus, adrenal gland, pituitary or hypothalamus which would contraindicate the use of gonadotropins.
12. Any abnormal finding of clinical chemistry, haematology or vital signs at screening, which is judged clinically relevant by the investigator.
13. Known moderate or severe impairment of renal or hepatic function.
14. Currently breast-feeding.
15. Undiagnosed vaginal bleeding.
16. Known abnormal cervical cytology of clinical significance observed within 3 years prior to screening (unless the clinical significance has been resolved).
17. Findings from the laboratory analyses at screening which preclude gonadotropin stimulation.
18. Findings at the gynaecological examination at screening which preclude gonadotropin stimulation.
19. Findings at the gynaecological examination at screening which are associated with a reduced chance of pregnancy, e.g. congenital uterine abnormalities or retained intrauterine device.

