6.2 Stimulation

6.2.1 Stimulation Day 1

Subjects will attend the stimulation day 1 visit on day 2-3 of the menstrual cycle.

The following must take place prior to randomisation:

- Ensure that the subject is still eligible for participation in the trial
- Check those inclusion and exclusion criteria that were not possible during screening
- Body measurements (body weight [*note*: this body weight result is used for dose calculation in the FE 999049 group])
- Urinary pregnancy test – must be negative
- Transvaginal ultrasound of uterus and ovaries (endometrial thickness, endometrial echogenicity pattern, ovarian volume, number and size of follicles)

If the subject fulfils all inclusion and exclusion criteria, she will proceed to randomisation:

- Randomisation, i.e. assignment to the lowest available subject number and thereby allocation to either FE 999049 or FOLLISTIM

The following must take place after randomisation but before administration of the first dose of FE 999049 or FOLLISTIM:

- Vital signs
- Blood collection for central laboratory analysis of endocrine parameters

Once the above has been completed, the following must be performed by the trial medication delegate. Care must be taken to ensure blinding of the investigator and other assessors.

- Dispense FE 999049 or FOLLISTIM according to randomisation and instruct the subject on how to administer FE 999049 or FOLLISTIM, including that all subsequent FE 999049 or FOLLISTIM administrations are preferably to be done in the evening
- Administer the 1st dose of IMP according to randomisation [administration of IMP takes place at the clinic and can be done by either the trial medication delegate or the subject under supervision by the trial medication delegate]:
 - If randomised to FE 999049; daily dose is calculated by the eCRF according to AMH level at screening and body weight at randomisation (see Table 5-1 on page 45 for detailed instructions)
 - If randomised to FOLLISTIM; starting dose for the first 5 days is fixed at 150 IU.
- Hand out the diary to the subject. The subject must be instructed to assess and record local tolerability immediately, 30 min and 24 hours after each injection of FE 999049 or FOLLISTIM throughout the entire stimulation period

After the first administration of FE 999049 or FOLLISTIM, the subject must do the following:

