7.1 Demographics and Other Baseline Characteristics

7.1.1 Demographics

Demographics and other baseline characteristics (body measurements, ultrasound parameters, vital signs, and endocrine parameters) obtained before first exposure to IMP will be listed by subject and presented in summary tables.

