The follicle cohort on stimulation day 6 and end-of-stimulation will be summarised by treatment on the follicle level (number of follicles 8-9 mm, 10-11 mm, 12-14 mm, 15-16 mm and ≥ 17 mm) and on the subject level (total number of follicles, size of largest follicle, average follicle size, average size of three largest follicles, and number of follicles ≥ 8 mm, ≥ 10 mm, ≥ 12 mm, ≥ 15 mm and ≥ 17 mm). Continuous data will be compared between treatment groups using van Elteren test stratified for AMH and within each AMH stratum using the Wilcoxon's test.

Fertilisation Rate

An oocyte is defined as fertilised if it is scored as 2 pronuclei at 19 hours. For subjects with oocytes retrieved, the rate of fertilised oocytes to oocytes retrieved (and also the rate of fertilised oocytes to metaphase II oocytes for those inseminated using ICSI) will be tabulated. Further, the number of fertilised oocytes per subject will be tabulated including both summary statistics and a frequency table. Number of fertilised oocytes, number of metaphase II oocytes, fertilisation rate, the rate of metaphase II oocytes to oocytes retrieved, and fertilisation rate relative to metaphase II oocytes will be compared between treatment groups using van Elteren test stratified for AMH and within each AMH stratum using the Wilcoxon's test. Note that the analysis of fertilisation rates excludes subjects without oocytes retrieved and do therefore not adhere to the randomisation principle.

Number and Quality of Embryos on Day 3

The number of embryos on day 3 including a breakdown by selected quality parameters will be tabulated including both summary statistics and frequency tables. Further, for subjects with oocytes retrieved, the rate of embryos to oocytes retrieved will be summarised overall and by selected quality parameters. Numbers and rates will be compared between treatment groups using van Elteren test stratified for AMH and within each AMH stratum using the Wilcoxon's test. Categorical data (subjects with at least one good-quality embryos) will be compared between treatment groups using a logistic regression model with treatment and AMH stratum as fixed factors and within each AMH stratum using the chi-square test.

Number and Quality of Blastocysts on Day 5

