The number of blastocysts on day 5 including a breakdown in quality scores will be tabulated including both summary statistics and frequency tables. The number of subjects with at least one good-quality blastocyst, i.e. of grade 3BB or higher, will be reported. Further, for subjects with oocytes retrieved, the rate of blastocysts to oocytes retrieved will be summarised overall and by quality score. Numbers and rates will be compared between treatment groups using van Elteren test stratified for AMH and within each AMH stratum using the Wilcoxon's test. Categorical data (subjects with at least one good-quality blastocyst) will be compared between treatment groups using a logistic regression model with treatment and AMH stratum as fixed factors and within each AMH stratum using the chi-square test.

Circulating Levels of Endocrine Parameters

Blood samples drawn at stimulation days 1 and 6 and end-of-stimulation are analysed for FSH, LH, estradiol, progesterone, inhibin A and inhibin B. Values below the lower limit of quantification (LLOQ) will be included as LLOQ/2. Values above the upper limit of quantification (ULOQ) will be included as ULOQ. For LH, progesterone and LH surge (both LH and progesterone) a summary table will be prepared displaying the proportion of subjects who have at least one markedly abnormal value. The table will also be produced based on data from day 6 only and for end-of-stimulation only. The markedly abnormal criteria is specified in [Appendix 1](#).

Each endocrine parameter and the change from baseline for post-baseline measurements will be tabulated for stimulation day 1 (baseline), stimulation day 6 and end-of-stimulation. Each parameter will be compared between treatment groups using an analysis of covariance model (ANCOVA). No subgroup analysis will be performed per age group. In this model ln-transformed measurements will be the dependent variable and the linear predictor will include treatment and AMH stratum as fixed factors and the baseline measurement (ln-transformed) as covariate. The estimated treatment ratio (FE 999049/FOLLISTIM) with 95% confidence interval will be presented accompanied by the p-value for test of no treatment difference.

10 Safety

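### The follicle-number comparisons ignore the follicle count taken before randomisation; the planned test is valid, but adjusting for that count could give more precision from data already collected.

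*SAP*

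**What the plan says.** SAP 9.4, under the number and size of follicles, sets the time points: "The follicle cohort on stimulation day 6 and end-of-stimulation will be summarised by treatment on the follicle level", and also on the subject level (total number, sizes, and counts at or above 8, 10, 12, 15 and 17 mm). The comparison is then specified: "Continuous data will be compared between treatment groups using van Elteren test stratified for AMH and within each AMH stratum" by Wilcoxon's test. Protocol 9.7.4 names the same tests. No baseline follicle variable enters.

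Protocol 6.2.1 introduces the day 1 steps with "The following must take place prior to randomisation", and one of them is "Transvaginal ultrasound of uterus and ovaries (endometrial thickness, endometrial echogenicity pattern, ovarian volume, number and size of follicles". The flow chart in Table 6-1 also marks the day 1 ultrasound as done before randomisation. The scan is needed for eligibility as well, since exclusion criterion 2 is "One or more follicles >10 mm (including cysts) observed on the transvaginal ultrasound prior to start of stimulation on stimulation day 1".

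SAP 7.1.1 covers "baseline characteristics (body measurements, ultrasound parameters, vital signs, and endocrine parameters) obtained before first exposure to IMP"; these are to be listed and summarised. The SAP gives the day 1 follicle count no other role.

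Later in SAP 9.4 the endocrine parameters are analysed by ANCOVA on the log scale, with "treatment and AMH stratum as fixed factors and the baseline measurement (ln-transformed) as covariate", and reported as a treatment ratio with 95% confidence interval.

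**The concern.** Comparing ovarian response is a secondary objective (protocol 2.1), and protocol 3.5.2 lists follicular development among the pharmacodynamic endpoints that describe it. The number of follicles visible before stimulation may well predict how many grow, beyond what two AMH classes capture. Treatment cannot have affected that number, because it is recorded before allocation. If it is prognostic, leaving it out gives up precision at no saving.

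The comparisons within AMH stratum have most to gain. In the overseas phase 3 trial described in protocol 1.1, the oocyte difference changed direction between strata (8.0 versus 7.0 with AMH below 15 pmol/L, 11.6 versus 13.3 at 15 pmol/L or above). If follicle numbers behave likewise, the pooled test partly cancels, and the information lies in stratum comparisons with roughly half the women each.

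The SAP already adjusts the endocrine endpoints for baseline, and gives no reason for treating follicle numbers differently.

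**Working it through.** **1. The plan's own figure.** The documents state no power, standard deviation or correlation for follicle endpoints. The only sample-size figure is for the primary endpoint (SAP 3.2: margin 3.0 oocytes, SD 8.1, one-sided 2.5%, 90% power). With the noncentral t distribution, power is 89.97% at 154 per group and 90.15% at 155, so 155 reproduces. Allowing for 5% major deviations, 155 / 0.95 = 163.2, rounded up to 164 per group and 328 in total. This also reproduces, and is used below only as the number of women.

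**2. Effect of adjustment.** Let ρ be the correlation, within AMH stratum, between the day 1 total count and the later follicle number. Adjustment multiplies the residual variance by 1 − ρ² and the confidence-interval width by √(1 − ρ²). The unadjusted analysis would need 328 / (1 − ρ²) women for the same precision. Because ρ is not in the documents, a range is assumed.

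Power is shown for a shift that has 80% power unadjusted with 164 per arm at two-sided 5%: (1.960 + 0.842) × √(2/164) = 0.31 SD. The last two columns come from a simulation with 4,000 runs per row, 328 women, two equal AMH strata and normal data (the last two being assumptions).

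| ρ | Variance factor | CI width factor | Equivalent total N | Power, normal approximation | Simulated power, van Elteren | Simulated power, rank ANCOVA |
|---|---|---|---|---|---|---|
| 0 | 1.00 | 1.00 | 328 | 80.0% | 78% | 78% |
| 0.2 | 0.96 | 0.98 | 342 | 81.6% | 78% | 79% |
| 0.3 | 0.91 | 0.95 | 360 | 83.6% | 77% | 80% |
| 0.5 | 0.75 | 0.87 | 437 | 89.9% | 78% | 87% |

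The planned test stays at 77–78% throughout, since ρ does not enter it. ANCOVA on the simulated values gave 80%, 81%, 83% and 89%.

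**3. Validity.** With no treatment effect and ρ = 0.5, the simulated two-sided error was 4.7% for van Elteren, 5.2% for rank ANCOVA and 5.0% for ANCOVA. All are close to 5%.

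**4. Within one stratum.** With an equal split, 82 women per arm, and an assumed shift of 0.25 SD, the noncentrality is 0.25 × √(82/2) = 1.60. Power is then Φ(1.60 − 1.96), about 36%. Dividing 1.60 by √(1 − ρ²) gives about 39% at ρ = 0.3 and 46% at ρ = 0.5.

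**5. Where a baseline exists.** Exclusion criterion 2 removes women with any follicle above 10 mm on day 1. Counts of follicles at or above 12, 15 and 17 mm are therefore zero at baseline by design, and the largest-follicle size is capped. The usable covariate is the day 1 total count. It may predict later numbers; the documents give no ground to expect that it predicts later sizes.

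**The case against.** The case for leaving the plan alone has several parts.

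- **The test is valid, and no formal claim rests on these endpoints.** SAP 9.1 presents the secondary endpoints as additional characterisation, without multiplicity control or a power target. This stands, and it makes the point one of efficiency. A reader might infer that chance imbalance in the day 1 count biases the comparison. It does not: the randomised test allows for chance imbalance, and the baseline ultrasound tables would show it.
- **The gain is undocumented.** This stands. Stratifying by AMH already captures some of the information, and only the correlation left within strata counts. At ρ = 0.2 the simulated gain is about one percentage point.
- **The endocrine analogy is imperfect.** There the same analyte is measured before and after. Here, much of the follicle list has no like-for-like baseline. Sizes at end-of-stimulation are also constrained by the triggering criterion in protocol 6.2.4. This stands for the size endpoints. For follicle numbers, a covariate need not be the same variable as the outcome to be useful.
- **Slopes may differ by arm.** One arm is dosed by AMH and body weight and the other starts at a fixed dose, so dependence on the day 1 count may differ. That would leave adjustment valid, but the tabulated gains might not carry over exactly.
- **The protocol also names the van Elteren test, and SAP section 12 declares no deviations.** This stands and affects how the change must be recorded.

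A reader might also infer that the SAP breaks its own rule on confidence intervals, since these rank tests give none. The documents do not support that: SAP 9.4 asks for intervals only where appropriate, and the SAP uses the same rank tests for fertilisation, embryo and blastocyst numbers.

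**Conclusion.** The observation holds for the follicle-number endpoints. A count that protocol 6.2.1 requires before randomisation is left out of the comparison, and using it could only help or be nearly neutral at this sample size. The gain is about 4%, 9% or 25% of the variance if the within-stratum correlation is 0.2, 0.3 or 0.5, and nothing if it is 0. These correlations are assumptions; the power figures also assume normal data, equal strata and a common slope in both arms.

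It would be too strong to say that a loss of precision is established, that the planned test is wrong, or that every follicle endpoint needs adjusting. The documents give no correlation, the planned test holds its error rate, and size endpoints lack a comparable baseline. The primary non-inferiority conclusion does not depend on this point.

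**What to change.** In SAP 9.4, for total follicle count and counts by size threshold on day 6 and at end-of-stimulation, add the stimulation day 1 total follicle count as a covariate, overall and within AMH strata. Either of two methods serves:

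- **Rank ANCOVA stratified for AMH.** Within each stratum, regress the ranked outcome on the ranked day 1 count, then compare the residuals between arms and combine across strata.
- **ANCOVA with treatment, AMH stratum and day 1 count**, dropping the stratum term for the within-stratum comparisons. This also gives an adjusted mean difference with 95% confidence interval.

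Keep the van Elteren and Wilcoxon tests alongside as the protocol specifies, or record their replacement in SAP section 12. For follicle-size endpoints, adjustment may be left optional and described as such.

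Settle the choice before unblinding; if the blind has been broken, label the adjusted analysis supplementary. No new data are needed. The cost is a few lines of SAP text and code and, if the tests are replaced, a documented change from the protocol analysis.

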6.4 Oocyte / Embryo / Blastocyst Evaluation

The laboratory procedures regarding handling and evaluations of oocytes, embryos and blastocysts are described in detail in a trial-specific manual. This section provides an overview of the procedures and assessments to be made from oocyte retrieval till transfer at the blastocyst stage. The flow of the trial procedures for embryos is shown in Table 6-2.

Table 6-2 Trial Flow Chart – Oocyte / Embryo / Blastocyst Procedures

| Timing | Day 0 (OR) | | Day 1 | Day 3 | Day 5 |
|---|---------------|----|---------------|---------------|-----------------|
| | -2h (± 2h) | 0h | 19h (± 2h) | 68h (± 2h) | 120h (± 3h) |
| Oocyte retrieval (OR) | X | | | | |
| Assessment of maturity stage (applicable for oocytes undergoing ICSI) | X | | | | |
| Insemination by IVF or ICSI | | X | | | |
| Assessment of oocyte fertilisation | | | X | | |
| Assessment of embryo/blastocyst quality | | | | X | X |
| Transfer of a single blastocyst ^{a)} | | | | | X |
| Cryopreservation of blastocysts | | | | | X ^{b)} |

a) In the absence of a viable blastocyst, a single morula may be used for transfer.

b) Cryopreservation may also occur after day 5.

Assisted hatching is prohibited and pre-implantation genetic diagnosis (PGD) / pre-implantation genetic screening (PGS) are prohibited.

Day 0 (Oocyte Retrieval)

- Oocyte retrieval at 2h (± 2h), i.e. 0-4 hrs, before start of any insemination procedure. Oocytes must be cultured individually in separate dishes / droplets
- Procedures between oocyte retrieval and insemination:
 - Assessment of maturity stage (applicable for oocytes undergoing ICSI)
- Insemination using IVF or ICSI using ejaculated sperm (fresh or frozen) from partner

Day 1 after Oocyte Retrieval

- Assessment of fertilisation (number of pronuclei) at 19h (± 2h) post-insemination

Day 3 after Oocyte Retrieval

- Assessment of embryo quality at 68h (± 2h) post-insemination

Day 5 after Oocyte Retrieval

- Assessment of blastocyst quality at 120h (± 3h) post-insemination
- Transfer of a single blastocyst at 120h (± 3h) post-insemination (section 6.5)

- Cryopreservation at 120h (\pm 3h) post-insemination, in line with local practice and declaration by JSOG [*note*: cryopreservation may also occur after day 5]

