7.4.13 Maturity Stage

Maturity stage will be assessed prior to insemination for oocytes that will undergo ICSI. Maturity stage will be categorised as germinal vesicle, metaphase I, metaphase II, degenerated or other.

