6.2 Full Analysis Set

The FAS is defined as all randomised and exposed (to IMP) subjects. Subjects will be analysed according to planned (randomised) treatment.

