9.4 Secondary Endpoints

Secondary efficacy endpoints will be evaluated based on the FAS only.

Statistical tests will be performed using a two-sided test at a 5% significance level. Treatment differences will (where appropriate) be presented with 95% confidence intervals and p-values

corresponding to the statistical test of the hypothesis of 'equal effect' against the alternative of 'different effect'.

Positive β hCG Rate

Positive β hCG is defined as positive serum β hCG test 13-15 days after transfer. The positive β hCG rate will be summarised and analysed in a similar manner as the clinical pregnancy rate.

Vital Pregnancy Rate

Vital pregnancy is defined as at least one intrauterine gestational sac with fetal heart beat 5-6 weeks after transfer. The vital pregnancy rate will be summarised and analysed in a similar manner as the clinical pregnancy rate. For subjects with a vital pregnancy, the number of intrauterine gestational sacs with fetal heart beat and the number of fetuses with fetal heart beat will be tabulated.

Implantation Rate

Implantation rate is defined as the number of gestational sacs 5-6 weeks after transfer divided by number of blastocysts transferred. The implantation rate will be summarised and analysed in a similar manner as the vital pregnancy rate. The transferred blastocysts are the experimental unit. Note that since single blastocyst transfer is mandatory in this trial, these descriptions and analyses are likely to be identical to a description and analysis of the clinical pregnancy rate in the subgroup of subjects that had a blastocyst transfer.

Cycle Cancellation due to Poor or Excessive Ovarian Response or Blastocyst Transfer Cancellation due to Excessive Ovarian Response / OHSS Risk

For this endpoint, treatment groups will be compared using a logistic regression model with treatment and AMH stratum as fixed factors. The difference between treatments will be reported as an odds ratio including 95% confidence interval and p-value for test of no treatment difference. In case of sparse data, treatments will be compared using the Cochran-Mantel-Haenszel test stratified for AMH stratum. Within AMH stratum the comparisons will be based on Fisher's exact test.

If both the factors treatment and AMH stratum are significant in the logistic regression analysis the possibility of a treatment-by-AMH interaction will be investigated.

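### SAP 9.4 compares metaphase II counts and rates on the FAS, but metaphase II status is recorded only for oocytes sent to ICSI

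*SAP*

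**What the plan says.** The Fertilisation Rate paragraph of SAP 9.4 sets out van Elteren tests stratified by AMH, and Wilcoxon tests within each AMH stratum, for a list that includes "Number of fertilised oocytes, number of metaphase II oocytes, fertilisation rate, the rate of metaphase II oocytes to oocytes retrieved". Fertilisation rate relative to MII closes the list. For the population, SAP 9.4 says "Secondary efficacy endpoints will be evaluated based on the FAS only", and SAP 6.2 says "The FAS is defined as all randomised and exposed (to IMP) subjects".

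ICSI appears once in that paragraph, in an earlier sentence and for one tabulated quantity: "and also the rate of fertilised oocytes to metaphase II oocytes for those inseminated using ICSI) will be tabulated". The one exclusion mentioned is "Note that the analysis of fertilisation rates excludes subjects without oocytes retrieved".

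Protocol 7.4.13 says where MII status comes from: "Maturity stage will be assessed prior to insemination for oocytes that will undergo ICSI", and "Maturity stage will be categorised as germinal vesicle, metaphase I, metaphase II, degenerated or other". Protocol Table 6-2 has the same limit: "Assessment of maturity stage (applicable for oocytes undergoing ICSI". Protocol 3.1.2 and 3.5.1 allow insemination by IVF or ICSI.

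For this endpoint, protocol 9.7.4 compares only the number of fertilised oocytes and the fertilisation rate. The SAP version history shows that the MII comparisons came in with version 2.0.

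**The concern.** The SAP plans a comparison on a population in which part of the data is never collected. An oocyte inseminated by IVF has no maturity record. The missing-data rules in SAP 9.1 cover the primary endpoint and the pregnancy and implantation endpoints, and say nothing about MII. The programmer is left to decide what an IVF-only subject contributes and which oocytes belong in the denominator.

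The second choice has a stated answer, all oocytes retrieved, and that answer is wrong for any subject with oocytes not sent to ICSI. The resulting figure mixes oocyte maturity with the share of oocytes given ICSI. A reader of the report would take it for a maturity rate. By default under SAP 9.1 the same comparisons are also run in three age groups, so the undefined variable enters several tables.

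**Working it through.** The plan gives no figure for these parameters, so there is none to reproduce. The check sets the texts side by side and then illustrates the size.

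**1. Which subjects have the data**

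| Subject | MII count | MII / all retrieved |
|---|---|---|
| All oocytes to ICSI | complete | correct |
| All oocytes to IVF | not recorded | cannot be derived |
| Oocytes divided between IVF and ICSI | partial (ICSI oocytes only) | understated |
| No oocytes retrieved | could be taken as 0 | undefined |

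The documents do not mention the third row. It is possible because maturity is assessed oocyte by oocyte and no text requires one method per woman.

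**2. Size of the error for one woman**

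Let m be the true MII proportion and s the share of her oocytes sent to ICSI. If the ICSI oocytes are typical of her oocytes, the expected planned rate is m × s, and the expected rate among assessed oocytes is m.

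- Worked case (assumed counts): 12 retrieved, 6 to ICSI, 5 of those MII. Planned: 5/12 = 42%. Among assessed: 5/6 = 83%.
- With m = 0.80 (assumed), the planned rate is 0.80, 0.60, 0.40 or 0.20 for s = 1, 0.75, 0.50 or 0.25.
- With s = 0.50 and m from 0.70 to 0.90, it runs from 0.35 to 0.45.

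**3. Could this create a difference between arms?**

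Only if s differs between arms. An illustrative simulation forces this by making splitting depend on yield. Assumptions:

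- mean yields from ESTHER-1 (protocol 1.1), FE 999049 v follitropin alfa: 8.0 v 7.0 for AMH <15 pmol/L and 11.6 v 13.3 for AMH ≥15 pmol/L
- negative-binomial counts with SD 0.55 × mean
- m = 0.80 in both arms
- 30% of women IVF-only (set to missing) and 40% ICSI-only
- 30% with half their oocytes sent to ICSI once yield reaches 10, and all sent to ICSI below that.

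| AMH stratum | FE 999049 | Comparator | Difference |
|---|---|---|---|
| <15 pmol/L | about 74% | about 76% | about −1.5 points |
| ≥15 pmol/L | about 70% | about 68% | about +1.5 points |

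With assessed oocytes as the denominator, every cell returns 80%. The main distortion is therefore in the level. With 328/4 = 82 women per arm and stratum (assumed equal strata), the standard error of each difference is about 4 points. The artefact is thus about 1.5/4 ≈ 0.4 standard errors, with opposite signs in the two strata.

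**4. How many women would have a complete count**

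If 25%, 50% or 75% of the 328 women are ICSI-only (assumed), about 82, 164 or 246 remain.

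**The case against.** The strongest reply is that MII first appears in the SAP paragraph tied to ICSI, so the authors may have meant the qualifier to carry forward; and naming the FAS does not create values that were never collected. The table shells and the laboratory manual are separate documents and may contain the derivation rule. This is fair as to intent. It does not settle the denominator: the SAP names all oocytes retrieved, and that stays wrong for a woman with both methods even if IVF-only women drop out.

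Four stronger readings are tempting, and the documents do not support them.

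- **IVF-only women will be scored as 0 MII oocytes.** No text says so. The zero rule in SAP 9.1 applies to oocytes retrieved, and the rule that treats unrecorded results as negative applies to the pregnancy and implantation endpoints.
- **Fertilisation relative to MII may exceed 100%.** That would require counting IVF-fertilised oocytes in a rate that the same paragraph has already tied to ICSI. What is missing is the qualifier in the comparison sentence.
- **The comparison is systematically biased between arms.** No passage makes insemination method depend on yield. Male factor infertility is an entry diagnosis in protocol 4.1.1, so a choice driven by sperm quality is just as plausible. In ESTHER-1, overall yields were 10.0 v 10.4 with no statistically significant difference, and this trial's sample size assumes equal effect.
- **Restricting the count to ICSI-only women solves the problem.** That restriction selects on a choice made after randomisation. Under the assumptions above, in the lower AMH stratum, mean MII counts in all-ICSI women are about 5.8 v 5.2, against true values of about 6.4 v 5.7. The restricted count should therefore be descriptive.

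**Conclusion.** The point holds as a mismatch between a planned analysis and the data collected. SAP 9.4 compares the MII count and the MII-to-retrieved rate on the FAS, while MII status exists only for ICSI oocytes. For IVF-only women neither parameter can be derived. For a woman with both methods, the stated denominator lowers the rate in proportion to the share of her oocytes not given ICSI, for example by half at a 50% share. How often this happens is unknown, because the documents give neither the insemination mix nor the frequency of divided cohorts.

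Any artefact between arms is likely small: about 1.5 points per stratum under assumptions chosen to produce one. MII count and rate are not among the listed endpoints. They are supplementary comparisons without multiplicity adjustment, and the primary endpoint and main conclusions are unaffected. The correction is still worth making, because the stated rule gives a wrong number and is cheap to change.

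**What to change.** In SAP 9.4, Fertilisation Rate:

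- Define the MII rate as MII oocytes divided by oocytes assessed for maturity, that is, those allocated to ICSI.
- Carry the ICSI qualifier into the comparison of fertilisation rate relative to MII: two-pronuclei oocytes from ICSI divided by MII oocytes.
- Treat women with oocytes retrieved but none allocated to ICSI as missing for all MII parameters, not as 0.
- Present the number of MII oocytes only for women with all oocytes allocated to ICSI, as a descriptive summary without a test.
- Label all MII analyses as non-randomised subsets, extending the caution that the SAP already gives for fertilisation rates.

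The cost is a few lines of SAP text and a programming filter. Oocytes are cultured individually under protocol 6.4, so oocyte-level derivation should be possible, provided the insemination method or the maturity record is held per oocyte. The downside is fewer women in these tables, and a subset formed after randomisation that cannot support a causal comparison.
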